Based on available PK and PARP inhibition data, and with the aim of optimizing drug exposure and biological effect, we amended the PBTC-027 trial to enroll additional patients at Dose Level 2 (ABT-888 at 25 mg/m² bid, TMZ at 135 mg/m²/day, for 5 days every 28 days) with close monitoring for CNS toxicity. Three additional patients were enrolled on Dose Level 2, and no DLTs were observed. Thus, Dose Level 2 (ABT-888 at 25 mg/m² bid, TMZ at 135 mg/m²/day, for 5 days every 28 days) is the recommended phase II dose (RP2D) for children with recurrent or refractory CNS tumors.

To date, a total of twelve patients on PBTC27 have been treated on RP2D, and except for one grade-4 thrombocytopenia and the grade-5 ischemic infarction seen in the first two patients, no other dose-limiting toxicities were reported.

2.3 Rationale

This will be a Phase I/II study of ABT-888 and concurrent radiation treatment, followed by maintenance with ABT-888 and TMZ, in children with newly diagnosed DIPG. Phase I of the study will be the dose-finding portion of the trial to determine the MTD/recommended phase II dose of ABT-888 that can be safely administered with radiation treatment. Dosing of ABT-888 during irradiation will start at 80% of the adult dose (100 mg bid) that has been safely tolerated (section 2.2.2 and 5.1.1.2). After completion of ABT-888 and radiation treatment, patients in Phase I of the study will continue with maintenance therapy, receiving ABT-888 and TMZ at the recommended phase II doses determined from PBTC-027 (section 5.1.3). Intra-patient dose escalation of TMZ will also be studied to optimize TMZ exposure for individual patients (section 5.1.3.1).

The Phase II study will commence once the MTD/recommended phase II dose of ABT-888 that can be safely administered with radiation has been determined from the Phase I study. All patients in the Phase II study will also continue with maintenance therapy, starting with ABT-888 and TMZ at the recommended phase II doses determined from PBTC-027. Intra-patient dose escalation of TMZ will continue to be studied unless excessive toxicities are observed (section 5.1.3.1). In the absence of excessive toxicities or disease progression, all patients can receive up to 10 courses of maintenance therapy. ABT-888 may be available for patients beyond the 10th course of maintenance if the patient is benefiting from the treatment, has at least clinical and radiographic stable disease at the end of course 10 and the investigator and subject agree to continue treatment for up to an additional 13 courses.

2.3.1 Rationale for ABT-888 and Radiation Therapy

Pre-clinical studies have confirmed ABT-888's radiation potentiation in several adult cancers, and we have shown similarly that ABT-888 treatment inhibited DSB repair and enhanced efficacy of radiation in pediatric CNS tumors, including GBM. It is therefore reasonable to study ABT-888 concurrently with irradiation in children with newly diagnosed DIPG tumors.

2.3.2 Rationale for ABT-888 and TMZ

TMZ treatment concurrently with radiation therapy and continuing as maintenance therapy for

six months is now the standard of care for adults with GBM. Although in children with highgrade glioma and DIPG, a COG clinical trial (ACNS0126) of TMZ and irradiation followed by maintenance TMZ has not demonstrated superior survival compared to historical series, we hypothesize that TMZ resistance may account for the lack of therapeutic benefit in the majority of patients. Several pre-clinical studies have demonstrated that PARP inhibition enhanced *in vitro* and *in vivo* TMZ cytotoxicity in multiple malignant glioma cell lines and xenograft models, and such enhanced TMZ cytotoxicity was observed despite enhanced MGMT expression and/or MMR deficiency,¹⁰⁻¹² two of the known tumor mechanisms for TMZ resistance. We have similarly demonstrated that ABT-888 enhanced TMZ efficacy in xenograft models of pediatric GBM. Collectively, available pre-clinical data suggest that PARP inhibition by ABT-888 may reverse TMZ resistance in pediatric gliomas.

2.3.3 Rationale for Targeting Children with Brainstem Gliomas

We and others have shown that PARP is highly expressed in pediatric GBMs and brainstem gliomas. As radiation treatment only leads to a transient response in these aggressive tumors, it is highly likely PARP over-expression, either at the time of diagnosis or in response to irradiation, contributes to apparent radiation resistance. We therefore propose to study the benefit of ABT-888, a PARP inhibitor, in overcoming the radiation resistance in pediatric DIPG.

2.3.4 Rationale for ABT-888 Dosing During Radiation

Although it appears that, from the adult clinical trials, ABT-888 administered concurrently with TMZ and irradiation is associated with dose-limiting hematologic toxicities, administration of ABT-888 concurrently with radiation therapy only has been well tolerated. No DLT was observed at 100 mg BID and cumulative radiation doses of 37.5 Gy and it is anticipated that the dose of 150 mg BID in adults will be declared tolerable by the end of October 2011 (

AbbVie Laboratories and [name], CTEP, personal communication). We therefore propose to start at the 80% of the adult dose (100 mg bid) that has been safely tolerated and allow for 2 dose escalations to reach a pediatric dose that is equivalent to 150 mg BID in adults.

2.4 Correlative Studies Background

2.4.1 Rationale for Biology Studies

2.4.1.1 Potential Mechanism of Resistance against PARP Inhibition

Pre-clinical studies have shown that ABT-888 induces SSB, collapses replication forks, and results in unrepaired DSB,¹³ but tumors capable of enhancing their DSB repair, e.g. by up-regulating HRR, may acquire resistance to PARP inhibition.¹⁴ Conversely, tumors with deficient DSB repair, e.g. BRCA1 or BRCA2 deficient breast or ovarian cancers, should be theoretically hypersensitive to PARP inhibition, whether as a single drug or in combination treatment, and this hypothesis has been confirmed pre-clinically¹⁵ and most recently in two clinical trials.^{16,17} Therefore, it is imperative to document the baseline and post-treatment DSB repair capability in tumors, as these molecular markers may predict sensitivity to PARP inhibitors such as ABT-888.

As outlined above, tumors with deficient DSB repair should be hypersensitive to PARP inhibition, whether as a single agent or in combination treatment, and conversely, tumors capable of enhancing their DSB repair may become resistant to PARP inhibition. We therefore propose to study the baseline and post-treatment DSB capability in patients' peripheral blood monocytes

(PBMC) and plan to correlate results retrospectively with clinical outcomes. We also propose to document pre- and post-treatment PARP activity in PBMC as a surrogate measure of ABT-888 biological activity in tumor. In tumors that are atypical appearing and must be biopsied and proven to be high-grade gliomas prior to patients' enrollment, we also propose to quantify PARP activity and DNA repair protein levels (Ku 70, Ku 80, DNA-PK, BRCA 1, BRCA 2, Rad51, and ATM) in either frozen tumors or FFPE samples. These molecular data will help in guiding the design of a future phase 3 clinical trial.

2.4.2 Rationale for Imaging Studies

If ABT-888 is effective in enhancing radiation effect in DIPG as we hypothesize, it is possible that the rate of pseudoprogression may be higher for this proposed study compared to historical series. In parallel with earlier pediatric DIPG trials, for patients showing possible tumor progression on MRI during the first 6 months after the initiation of ABT-888 and irradiation (on required MRI studies performed at weeks 10, week 18, or 26), the treating physician will have the option of allowing the patient to remain on study, continuing protocol therapy, and repeating disease reassessment in 4-6 weeks. Provided that the patient does not show clinical deterioration consistent with tumor progression, has been on a stable or declining dose of steroids, and the subsequent MRI demonstrates tumor regression or stable disease, then the patient will remain on study and continue protocol therapy, and the frequency of subsequent MRI will revert to prespecified intervals. If the repeat MRI after 4-6 weeks shows disease progression, rather than pseudo-progression, then the time of progression will be the date of the initial MRI, not the follow up scan.

Key to assessing disease course and potential pseudoprogression is inclusion of detailed clinical data documenting each patient's status at the time of scheduled imaging or upon institutional call of "progressive disease." The ability to track neurologic status, symptoms or signs potentially heralding or reflecting progressive disease, or apparent neurologic stability is important in correlating clinical status with imaging findings, and documenting the clinical and/or imaging findings that prompt the investigator to call "progressive disease." We recently documented a relationship between tumor volume and diffusion (measured by serial echoplanar diffusion imaging) prior to and immediately after irradiation in a cross-protocol analysis of prior PBTC newly diagnosed DIPG patients. Tumors with larger diffusion values seemed to respond early to radiation therapy and percent reduction in ADC values correlated with both progression-free and overall survival rates.¹⁸ Tracking MR imaging volumetric, serial findings in the context of a phase II study of tipifarnib and irradiation showed pseudoprogression in just one of the 40 patient's studied.¹⁹

As a secondary objective, we shall study relative cerebral blood volume (rCBV), vascular permeability (K^{trans}) along with both fractional plasma volume (v_p) and the extravascular volume fraction (v_e), and the apparent diffusion coefficient (ADC) as parameters hypothesized to differentiate pseudoprogression from true early disease progression (PD). These parameters will be studied with serial imaging over the first 6 months after the initiation of ABT-888 and irradiation; quantitative MR metrics will be retrospectively correlated with clinical outcomes to study if they reliably distinguish pseudo-progression from early PD.

Recent preliminary work with adult glioblastoma patients has shown the potential of MR

perfusion and permeability imaging to differentiate between pseudoprogression and true early progression.²⁰⁻²⁵ True early progression appears to demonstrate increased relative cerebral blood volume and permeability compared to pseudoprogression.

While there appears to be some controversy regarding the utility of diffusion weighted MR imaging in the context of pseudoprogression, there is evidence to suggest that ADC values can be used to differentiate residual/recurrent tumor from necrosis.²⁶ This is predicated upon the idea that successful therapy will show increased ADC values secondary to a decrease in cellularity and an increase in the extracellular space.

We hypothesize that in the first 6 months following treatment with ABT-888 and concurrent radiation therapy, pseudoprogression will be marked by significantly lower relative cerebral blood volume (rCBV) compared to that seen in true early progression. T2*-weighted dynamic susceptibility-contrast MR imaging will be acquired to determine serial rCBV values.

In addition, we hypothesize that pseudoprogression will demonstrate significantly lower vascular permeability (K^{trans}) and fractional plasma volume (v_p) compared to cases with true early progression. The lower v_p is postulated to be the result of the absence of angiogenesis that typically characterizes progressive tumor. Extravascular extracellular space volume fraction (v_e) will likely be significantly higher in pseudoprogression versus true early progression. This is postulated to be the result of a decrease in cellularity and an increase in the extracellular space seen in necrosis. T1-weighted dynamic contrast enhanced MR imaging will be used to determine the K^{trans}, v_p , and v_e values serially during the first 6 months after irradiation and ABT-888.

We also hypothesize that pseudoprogression will be associated with significantly higher ADC values compared to those seen in true early progression. Using diffusion tensor MR imaging, we shall determine the ADC values of pseudoprogression and true early progression in the first 6 months following therapy and shall assess ADC values over time using DTI.

Short and long-term effects of irradiation on the brainstem structures will be assessed using diffusion tensor imaging. Previous work has shown that radiation therapy affects the white matter anisotropy.²⁷⁻²⁹ Changes have been noted in the brainstem, following treatment for posterior fossa tumors arising outside brainstem itself.³⁰ Diffusion tensor imaging will be used to assess the fractional anisotropy and ADC values within the tumor, within the white matter of the pons, and within the uninvolved midbrain and medulla.

2.4.3 Rationale for Pharmacokinetic Studies

Based on pre-clinical data demonstrating ABT-888's radiation potentiation in pediatric CNS tumor models and adult phase I clinical data, we will be administering ABT-888 at doses higher than 50 mg/m²/day (the highest dose studied in PBTC-027) concurrently with radiation therapy. It would be imperative that we characterize PK profile of ABT-888 when given at higher doses in combination with radiation therapy, especially if unanticipated toxicities are encountered. Furthermore, these PK data will be critical in optimal planning of a future phase III study. Therefore, PK studies for ABT-888 during radiation therapy will be **REQUIRED FOR THE PHASE I STUDY**. PK studies for ABT-888 during radiation for the Phase II study will also be performed but will be **optional**.

2.4.4 Rationale for Urine Correlative Study

Despite recent advances in the imaging and treatment of brain tumors, the ability to prospectively screen for new tumors or to detect tumor recurrence remains limited. Clinicians need to know when a tumor is present and – if previously treated – whether recurrence or tumor progression is occurring in order to most effectively direct therapy. For some of the most common pediatric brain tumors, such as medulloblastoma, ependymoma and juvenile pilocytic astrocytoma, patient outcome is closely linked with extent of resection.³¹⁻³⁶ Timely diagnosis of the presence of disease – including recurrence - is of particular importance in the brain, where radical maneuvers to contain tumor spread are often not possible because of eloquent neural tissue. Clinical detection (through observation of neurologic deterioration) of recurrent brain tumors is twice as likely as asymptomatic radiographic recurrence, yet for patients with recurrence detected radiographically before symptoms became present – the patients with early detection who are less likely to have widespread tumor dispersal - had better survival.³⁷ Thus, earlier detection of recurrence could improve patient outcomes by identifying the mass when it is small, before tumor cells have migrated, increasing the chances for a curative surgical resection.

[figure not shown]
Unfortunately, certain subtypes of brain tumors remain challenging to treat at any time due to growth within sensitive parts of the brain or intrinsic biologic characteristics conferring resistance to therapy. Yet even with these types of tumors, such as diffuse intrinsic pontine gliomas (DIPG) and glioblastoma multiforme (GBM), the ability to identify tumor status and response to therapy or progression is important so that clinicians provide patients and families with accurate prognostic information.

We therefore propose to study the feasibility of a novel, non-invasive method employing urinary biomarkers to detect the presence, progression and response to therapy of pediatric brain tumors. Studies from our laboratory, now confirmed by others, support the premise that tumor stage and progression may correlate with urinary levels of specific biomarkers,^{38,39} specifically that biomarkers related to regulation of vascular stability in the urine of affected patients might represent a novel, non-invasive method of detecting disease status, progression and therapeutic efficacy.³⁸⁻⁴² Our biomarker selection has been based on targeting specific tumor-related molecules and pathways, in contrast to other more general methods of high-throughput proteomic analyses.

Current methods of brain tumor diagnosis and follow-up center around the use of infrequent clinical examinations and expensive radiographic studies, such as computerized tomography (CT) and magnetic resonance imaging (MRI) that often require sedation or anesthesia in children. By contrast, urine collection carries no risks to the patient and is far less expensive (100-fold less than MRIs) so it can easily be done at frequent intervals, potentially enabling earlier detection of recurrent disease and dynamic evaluation of response to therapy. Urine collection is easy, non-invasive, and can be done locally, saving families travel to tertiary care centers. Analysis is rapid, with a turnaround time of 24 hours. Test results are numerical and are compared to specific statistical cutpoints, obviating the need for analysis that relies on subjective measures, such as film review or tissue staining. Additionally, biomarkers provide a method of assessment that relies on metabolic activity; a different – and complementary – approach to the current method of neuroimaging evaluation.

2.4.4.1 Preliminary data

We reported the first demonstration of the utility of urinary biomarkers in brain tumors, including the use of molecules specifically related to the regulation of vascular stability⁴³ and recently published a proof-of-principle case series, that specifically evaluated the ability of a panel of urinary biomarkers such as MMP-2, MMP-9, NGAL and VEGF (See Figure 4 and **Table 6** and **Table 7**).⁴⁴ The results of this series support the premise that levels of urinary biomarkers can not only predict the presence of brain tumors but also that they change in response to effective surgical therapy (see Figure 5).

We have subsequently identified additional biomarkers that can be detected in urine in association with pediatric brain tumors. These new markers (HB-EGF, EGF, HGF and TIE-2) allow for greater sensitivity in identifying the presence of disease. Specific to this project, these markers have been evaluated in pediatric patients with various subtypes of high grade glioma, including both GBM and anaplastic astrocytoma.

Table 6								
Demographics, MMP's and VEGF for Brain Tumor Patients and Controls								
Variable	Contro	ol Group ((n=23)	Brain T	`umor Group	o (n=28)	Р	
	Median	IQR	Range	Median	IQR	Range		
Age, yr	22	4-55	0-71	32	8-58	1-73	0.37	
MMP-9	0	0-0	0-6	0.6	0-5.7	0-294	< 0.001*	
MMP-9/NGAL	0	0-0	0-12.8	0.8	0.2-1.0	0-1.1	< 0.001*	
MMP-2	0	0-0	0-3	4.3	0.8-8.8	0-27	< 0.001*	
VEGF	25	0-250	0-391	753	451-957	25-4462	< 0.001*	
Female sex, no. (%)	11(48)				13 (46)		0.92	

T 11 (

Table '	7
---------	---

Results of Receiver Operating Characteristic (ROC) Curve Analysis and Diagnostic Performance Indices of MMP-2 and VEGF							
	01 NIN	P-2 and VEGF					
Biomarker	AUC	95% CI	P value				
MMP-2 (ng/ml)	0.894	0.800-0.987	< 0.0001				
VEGF (pg/L)	0.965	0.913-0.999	<0.0001				
Cutoff Points	Sensitivity (95% CI)	Specificity (95% CI)	Accuracy (95% CI)				
MMP-2 >0.4 ng/ml	82.1 (65.2-94.0)	95.7 (78.1-99.9)	88.2 (76.1-95.6)				
VEGF >350 pg/L	95.2 (76.2-99.9)	89.5 (66.9-98.8)	92.5 (80.0-98.5)				

2.4.4.2 Selection of Brainstem Glioma

The proof-of-principle data described above suggests that urinary biomarkers may have potential to identify the presence of brain tumors. Further validation of this hypothesis would be bolstered by increasing the number of patients studied and following individual patients longitudinally to evaluate whether changes in disease status (response to therapy or progression) are reflected in corresponding changes in biomarker levels.

This project will focus on urinary biomarker levels in children with brainstem glioma. These patients represent a relatively homogenous population, minimizing variability in age (children), tumor pathology (high grade glioma), location (pontine, without concern for dissemination within the neuraxis) and treatment regimens. As these lesions are not treated with surgical excision, the imprecision inherent to measuring the degree of resection will not be present. The near-uniform progression of these tumors within a short window of time (>80% of patients manifest disease progression within 1 year) allows for data to be collected within a manageable time frame. In combination, these characteristics support the use of this group as an ideal study population.

2.4.4.3 Justification for Data Collection

One of the objectives of this study is to identify whether biomarker levels correlate with changes in tumor status. In order to accurately reflect current practice, we will collect clinical data (as measured by Karnofsky and Lansky scores) and several different types of radiographic measures, including changes in size, altered enhancement pattern and the radiologist's overall assessment of tumor status.

Control urines will be obtained from a pre-existing, institutional review board approved urine bank in the Vascular Biology Program at Children's Hospital Boston. These samples come from children with radiographic evaluation of their central nervous system by MRI. Children may

have no evident pathology or evidence of congenital fatty fila (thickening of the terminal end of the spinal cord) or Chiari I malformation (herniation of the cerebellar tonsils below the foramen magnum). No patients have radiographic or clinical histories of tumor, recent trauma, hydrocephalus or arteriovenous malformation (AVM). We currently have control samples from approximately 50 children and collect 1-2 additional samples per week. Thus we anticipate that at the time of analysis we will have a large number of control samples with adequate diversity to enable us to match each clinical sample with an age- and sex-matched control.

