3.1.5 Prior Therapy

Patients must have not received any prior therapy other than surgery and/or steroids.

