3.2 Exclusion Criteria

3.2.1 Concurrent Illness

Patients with any clinically significant unrelated systemic illness (serious infections or significant cardiac, pulmonary, hepatic or other organ dysfunction), that would compromise the patient's ability to tolerate protocol therapy or would likely interfere with the study procedures or results.

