13.4.3 Urine Biomarkers

Comparison of Urine Biomarker Levels in Patients vs. Controls:

In order to determine whether the levels of these urinary biomarkers are elevated in DIPG patients, we will compare median levels for tumor patients to levels in healthy age- and gendermatched controls using the Mann-Whitney U-test. Despite the presence of matched controls, Mann-Whitney U-test allows us to utilize a conservative approach compared to the Wilcoxon signed-rank test since matching by age and gender is done to reduce variability rather than to facilitate the use of methods for paired data. In addition, the percentage of patients and controls above the previously established cut-off values for each urinary biomarker will be compared using the chi-square test. Based on a preliminary power analysis for this chi-square test a sample

size of 58 brain tumor patients and 58 controls will provide 80% power with a conservative twosided alpha level of 0.01 in capturing a difference of 30% between the groups with respect to each urinary biomarker. We will also utilize ROC analysis for each biomarker in exploring various cut-points for differentiating between the control subjects and DIPG patients. Multivariable logistic regression models coupled with ROC analyses will be used to select a combination of these biomarkers in an attempt to improve their collective performance as a classifier.

Longitudinal Assessment of Changes in Biomarker Values and Their Association with Outcome: Using the data for patients who progress, for each biomarker we will compare the levels at baseline with levels at progression as determined by MRI to assess whether the biomarker values change and if so by how much. This will be done via Wilcoxon signed rank test and exact confidence interval estimates of the percent change. We will also tabulate the percentage of patients who have biomarker levels above the previously established cut points for each biomarker at baseline and at the time of progression. We will investigate whether the percentage of patients who are above/below the cutpoints for each of the biomarkers is different between baseline and time of progression via the McNemar's test. Provided adequate number of responses is present to make such analyses meaningful, we will also perform similar analyses comparing biomarker levels at baseline and at the time of response.

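### The urine case-control comparison uses controls screened free of hydrocephalus and recent trauma, but patients are not screened for these, so a difference could partly reflect factors other than the tumour

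*Combined protocol and SAP*

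**What the plan says.** **Controls.** Section 2.4.4.3 states: "Control urines will be obtained from a pre-existing, institutional review board approved urine bank". The bank belongs to one hospital, and its donors are children who had an MRI of the central nervous system. They may "have no evident pathology or evidence of congenital fatty fila" or a Chiari I malformation. The exclusions are: "No patients have radiographic or clinical histories of tumor, recent trauma, hydrocephalus or arteriovenous malformation (AVM"). Section 13.4.3 nevertheless describes the comparison as against "levels in healthy age- and gendermatched controls".

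**Patients.** Section 3.1.5 reads: "Patients must have not received any prior therapy other than surgery and/or steroids". Sections 3.1 and 3.2 contain no criterion on hydrocephalus or recent trauma. The nearest exclusion, in 3.2.1, covers "Patients with any clinically significant unrelated systemic illness (serious infections or significant cardiac, pulmonary, hepatic or other organ dysfunction"). Section 9.1.4.1 schedules a pre-treatment urine at enrolment, which can follow surgery and steroids.

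**Analysis.** Section 13.4.3 will "compare median levels for tumor patients to levels in healthy age- and gendermatched controls using the Mann-Whitney U-test", then compare the proportions above a cut-off by chi-square, explore cut-points by ROC, and combine markers by logistic regression. Age and gender are the only matching factors. No stratified, adjusted or sensitivity analysis covers hydrocephalus, surgery or steroids.

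**Assay.** Section 9.1.4.5 states blinding of the examiner for zymography. It states none for the ELISA, which supplies the quantitative levels of all 8 markers.

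**The concern.** In a case-control comparison, anything that differs systematically between the groups is a competing explanation for the result. Here patient status is tied to several such factors:

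- hydrocephalus, which is excluded by design in controls and not in patients;
- prior surgery and steroid treatment, which are allowed in patients;
- sample source, which is one bank for controls and shipment from the participating sites for patients.

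Matching on age and gender removes none of these, and a larger sample would only estimate the mixed difference more precisely. At stake is what can be said about a marker, cut-point or classifier that separates the groups. As planned, it would be evidence that DIPG patients differ from screened bank controls, not that the tumour explains the difference. Calling the controls healthy makes the over-reading more likely.

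**Working it through.** **Step 1: the plan's own figure.** Section 13.4.3 gives 58 per group, 80% power, two-sided alpha 0.01 and a 30-point difference. It states no base rate. With the pooled-variance formula and 20% v 50% (mean 0.35):

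n = [2.576 × √(2 × 0.35 × 0.65) + 0.842 × √(0.2 × 0.8 + 0.5 × 0.5)]² / 0.30² = (1.737 + 0.539)² / 0.09 ≈ 57.6, so 58 per group, with power 80.4%.

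At 35% v 65% the same formula needs 64, and 58 gives 75.4%. The stated figure is reproducible and is not the problem.

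**Step 2: how large a false difference could be in the chi-square comparison.** Assume no tumour effect. Let p0 be control positivity, f the share of patients with a condition other than the tumour that affects the marker, and q the positivity among them. Then:

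apparent difference = p0(1 − f) + qf − p0 = f(q − p0).

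For p0, use 1 − specificity in Table 7 (section 2.4.4.1): MMP-2 100 − 95.7 = 4.3%; VEGF 100 − 89.5 = 10.5%. Those controls had a median age of 22 years (Table 6), so these rates are only indicative. The values of f and q are **assumptions**; the documents give neither.

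| f | q | False difference, p0 = 10.5% / 4.3% | Chance of a significant patient-higher result, p0 = 10.5% / 4.3% |
|---|---|---|---|
| 10% | 50% | 4.0 / 4.6 points | 3% / 6% |
| 20% | 80% | 13.9 / 15.1 points | 27% / 48% |
| 30% | 80% | 20.9 / 22.7 points | 58% / 80% |
| 50% | 80% | 34.8 / 37.9 points | 96% / 99% |

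Without bias, the chance in that direction is 0.01 / 2 = 0.5%. Example: 0.3 × (0.8 − 0.043) = 0.227.

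**Step 3: the comparison of levels.** For a normal shift of d standard deviations, the Mann-Whitney noncentrality is d × √(58/2) × √(3/π), and the test rejects when |Z| > 2.576.

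| Assumed d | Noncentrality | Chance of rejection (nominal 1%) |
|---|---|---|
| 0.2 | 1.05 | 6% |
| 0.3 | 1.58 | 16% |
| 0.5 | 2.63 | 52% |

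A mean shift of 0.3 SD arises, for example, if 30% of patients have a condition that adds 1 SD (0.30 × 1). The normal-shift model suits the MMPs poorly: Table 6 shows control MMP values with median 0 and interquartile range 0-0, so ties will be heavy.

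**Step 4: direction.** Both tables assume the factor raises the marker. If it lowers the marker, or if patient samples lose activity in handling, the bias reverses and could hide a real elevation.

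**The case against.** The strongest reply is that nothing in the documents links hydrocephalus, trauma, surgery or steroids to any of the 8 markers, or says how often patients have them. That stands. A reader might infer that raised markers with other causes will be credited to DIPG; the documents support only that they could be.

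Hydrocephalus in a child with a pontine tumour may result from the tumour, and section 5.3.1 has steroids given for edema and mass effect. That also stands. Removing such patients may remove part of the disease effect, so a restricted result cannot be the sole arbiter. It still bears on how specific a marker can be shown to be.

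Surgery may be uncommon. Section 3.1.2 enrols typical DIPG without histology and requires biopsy only for atypical tumours, and section 2.4.4.2 notes that these lesions are not excised. This limits the likely size of the effect, but 3.1.5 still permits surgery. It would also be too broad to say that patients are unscreened, since 3.2.1 excludes significant unrelated systemic illness.

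A reader might infer from section 9.1.4.2 that shipping raises patient values. It does not say so. It warns of degradation in the warm and requires ice and freezing, and degradation would lower values. The bank's own handling is not described, so a handling difference is possible but not shown.

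Finally, the assumed shifts are modest beside the earlier series: d = 0.3 corresponds to an AUC of Φ(0.3/√2) ≈ 0.58, against 0.894 and 0.965 in Table 7. This is a fair caution, although that series was not confined to children or DIPG.

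**Conclusion.** The concern holds in a limited form. Screening is one-sided, matching covers age and gender only, and no planned analysis separates tumour from hydrocephalus, surgery, steroids or sample source. The patient-control difference, the ROC cut-points and the logistic classifier share this limitation.

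The size is unknown. Under the assumptions shown, the false difference runs from 4 points to 38 points, the upper end exceeding the 30-point target. These are sensitivity figures, not predictions, and the direction is not fixed either. I take the patient sample to be the enrolment urine, because section 13.4.3 does not name the time point for this comparison.

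A reader might infer that the whole urine study or the trial's main result is compromised. The documents do not support that. Baseline against progression, baseline against response, and the PFS and OS associations use patients only, and the primary OS endpoint is untouched. Control numbers are not the difficulty: section 2.4.4.3 says "We currently have control samples from approximately 50 children and collect 1-2 additional samples per week", so reaching 58 takes about (58 − 50)/2 = 4 to (58 − 50)/1 = 8 weeks, before matching. This is a worthwhile, low-cost improvement to an exploratory objective.

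**What to change.** **1. Sensitivity analysis (13.4.3).** For each enrolment urine, flag hydrocephalus (from the baseline MRI), surgery before the sample, and steroid use. Repeat the patient-control comparison and ROC without patients who have hydrocephalus or recent surgery, and show results by steroid use. Report estimates and confidence intervals beside the main analysis. Do not make it a pass/fail rule, because a real marker could fail on lost numbers alone.

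**2. Assay (9.1.4.5).** Run each patient sample and its matched control on the same ELISA plate, in random order, with the operator blinded as already stated for zymography.

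**3. Wording (13.4.3).** Replace healthy with the control definition in 2.4.4.3, and limit the conclusion to DIPG patients versus screened, tumour-free controls.

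**Cost.** Baseline MRI (9.2.1), medical history (Tables 18 and 19) and steroid use (5.3) are already collected, although a hydrocephalus item must be added to the analysis data. Plates need some scheduling. No new visits or patient samples are needed.

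The restricted set is less precise. If 30% of 58 patients were dropped (58 × 0.7 ≈ 41), the 95% half-width for 50% v 20% would grow from 1.96 × √(0.25/58 + 0.16/58) = 16.5 points to 1.96 × √(0.25/41 + 0.16/58) = 18.4 points. Power at alpha 0.01 would fall from 80% to about 72% with all 58 controls kept, or 61% with 41 v 41. Participation is optional (9.1.4), so actual numbers may be smaller.
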